#### **3.4.5.2 Laboratory tests Results**

This section will describe the summary of safety lab test results. Summary of PK and PD results are described in previous section (3.4.4.1 and 3.4.4.2).

All safety lab test results will be listed. Additionally, each Lab Test results of each subject at different time points will be plot against the time points to show the trend.

The change of baseline of any numeric safety lab results will be for each treatment arm.

The change of severity (normal/abnormal) status of each safety lab results along time will also be summarized for each treatment arm.

#### **3.4.5.3 Vital Sign**

Vital sign at each time point and the corresponding Change from (section 3.3.4.2) baseline will be presented descriptively by treatment arm.

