##### 3.1.4 Dose Limiting Toxicity (DLT) Criteria

A potential DLT is defined as any of the following EXT608 TEAEs that occurs during the DLT period, graded according to the NCI Common Terminology Criteria for Adverse Events (CTCAE), Version 5.0 (2):

- Grade = 3 TEAE
- Grade = 3 anemia
- Grade = 3 AST/ALT elevation; and/or
- Grade = 2 AST/ALT elevation and Grade = 2 Bilirubin elevation

- Grade = 3 QTc prolongation
- Grade = 3 Hyper- and/or Hypotension
- Grade = 2 Hyperparathyroidism
- Grade = 2 Hyperthyroidism
- Grade = 3 Hypercalcemia
- Grade = 3 Hypocalcemia
- Grade = 3 Hypophosphatemia
- Grade = 3 Hypomagnesemia
- Grade = 3 Creatinine increased

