  - e. 6 months - fluoride tablets, oral bisphosphonates, methotrexate, growth hormone, digoxin, raloxifene or similar selective estrogen receptor modulators (SERMs)
  - f. 12 months - intravenous bisphosphonates
9. Participant is pregnant, nursing, or planning a pregnancy during the course of or within 3 months of completing this study.
10. Participant is male and intends to donate sperm before 90 days after study drug administration.
11. Participant has a history of cancer or other malignancy, with the exception of basal cell carcinoma that has been in remission for at least 5 years prior to Day -1.
12. Participant has a positive test result for hepatitis B surface antigen (HBsAg), hepatitis C virus (HCV) antibody or a human immunodeficiency virus (HIV) infection at Screening.
13. Participant has used nicotine-containing products (including but not limited to cigarettes, electronic cigarettes, pipes, cigars, chewing tobacco, nicotine patch or

nicotine gum) within 28 days prior to Inpatient Check-in (Day -1) or a positive urine cotinine test at Screening or Inpatient Check-in (Day -1).

14. Participant has poor peripheral venous access.
15. Participant has donated or lost 450 mL or more of their blood volume (including plasmapheresis) or had a transfusion of any blood product, within 45 days prior to Day 0.
16. Participant has a Screening or Inpatient Check-in (Day -1) abnormal (CS) ECG.  
Entry of any participant with an abnormal (NCS) ECG must be approved and documented by signature by the Investigator or medically qualified sub-investigator.
17. Participant has a resting blood pressure outside the ranges of 90 to 140 mm Hg for systolic and 55 to 90 mm Hg for diastolic, confirmed with repeat per Investigator discretion, at the Screening Visit or Inpatient Check-in (Day -1).
18. Participant has a resting heart rate outside the range 40 to 90 bpm, confirmed with repeat per Investigator discretion, at the Screening Visit or Inpatient Check-in (Day -1).
19. Participant has increased CV proarrhythmic potential (3):
  - a. Participant has a QT interval with Fridericia's correction method (QTcF) >450 ms (males) or >450 ms (females) or PR outside the range of 120 to 220 ms, confirmed with one repeat testing, at the Screening Visit or Inpatient Check-in (Day -1) Visit.
  - b. A history of additional risk factors for TdP (e.g., heart failure, hypokalemia, family history of Long QT Syndrome).

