### 8.3 Data Analysis

AEs will be presented in listings and Treatment Emergent Adverse Events (TEAEs) will be summarized. Individual results of laboratory tests (hematology, chemistry, and urinalysis) will be listed and change from baseline will be summarized using shift tables. Individual results of vital signs will be listed and observed values and changes from baseline will be summarized.

Individual results of quantitative ECG parameters from the 12-lead safety ECGs will be listed and observed values and changes from baseline will be summarized and analyzed consistent with the ICH E14 (3).

All summaries will be performed by placebo and each EXT608 dose level. Placebo data will be pooled across cohorts. Physical exam findings will be presented in data listings.

Concentrations of EXT608 will be summarized by dose over each scheduled sampling time using descriptive statistics. Individual plasma concentration data versus time will be presented in a data listing. PK parameters will be summarized by dose using descriptive

statistics. Dose proportionality will be assessed graphically and using a power model. PD will be presented in listings and summarized by dose and time point.

Detection of ADA and NAbs will be presented in listings and summarized by dose and time point.

No formal hypothesis testing will be conducted as part of this study.

DMB data packages will be based on the FAS for safety and PP for PK/PD.

Further details are described in the Statistical Analysis Plan.

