## 1.2 OBJECTIVES

### 1.2.1 Primary Objective

The primary objective is to characterize the safety and tolerability profile of escalating dose levels of EXT608 when administered to healthy adult participants as a single injection as assessed by:

- Incidence, nature, and severity of adverse events (AEs) and withdrawals due to treatment emergent AEs (TEAEs) [Time Frame: Day 0 up to Day 28]
- Frequency and severity of post-dose change from baseline in hematology, serum chemistries, urinalysis, electrocardiogram (ECG), vital signs, and physical examination (Exam) findings [Time Frame: Day 0 up to Day 28]
- Percentage of participants with injection or infusion site reactions [Time Frame: Day 0 to Day 7]

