#### 3.3.4.2 *Vital Signs*

Change from baseline will be calculated for vital sign from Day 0 to Day 28.

- Baseline will be the vital signs collected at Day 0 -90 pre-dose
- If Day 0 -90min vital signs are missing, then the vital signs on Day -1 will be considered as baseline. If the vital sign on Day -1 is also missing, then the change from baseline will be set as missing.

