## EXTBIO EXT608-101 Statistical Analysis Plan, V2, 2023-JULY-04

### 3.4 STATISTICAL METHODS

#### 3.4.1 General Considerations for all analyses

Unless specified, the following will apply to all summary tables:

- Continuous variable descriptive summary will include N, Mean, median, standard deviation, maximum and minimum.
- Categorical variable descriptive summary will include Total, count, and percentage.

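### The primary objective asks how often and how severely vital signs change, but the SAP plans no participant-level summary of either by dose

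*SAP*

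**What the plan says.** - **Objective.** SAP 1.2.1 (and Protocol 2.1) sets as the second primary measure "Frequency and severity of post-dose change from baseline in hematology, serum chemistries, urinalysis, electrocardiogram (ECG), vital signs, and physical examination (Exam) findings", over Day 0 to Day 28.
- **Derived variable.** SAP 3.3.4.2: "Change from baseline will be calculated for vital sign from Day 0 to Day 28". The baseline is the reading 90 minutes before dosing, with Day -1 as fallback. No other vital-sign variable is derived.
- **Analysis.** SAP 3.4.5.3: "Vital sign at each time point and the corresponding Change from (section 3.3.4.2) baseline will be presented descriptively by treatment arm".
- **Meaning of a descriptive summary.** SAP 3.4.1: "Continuous variable descriptive summary will include N, Mean, median, standard deviation, maximum and minimum".
- **Protocol counterpart.** Protocol 8.3: "Individual results of vital signs will be listed and observed values and changes from baseline will be summarized". SAP 1.4 declares no departure from the protocol's statistical section, so the listing stands.
- **Other parts of the same measure.** Safety laboratory results get normal/abnormal status changes summarised by arm (SAP 3.3.3.5.2, 3.3.4.4, 3.4.5.2). Physical examination gets normal/abnormal transition categories by arm (SAP 3.3.1, 3.4.3.3). Vital signs get no category.

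**The concern.** A frequency needs a number of participants affected, and a severity needs a size or grade for each participant. SAP 3.3.4.2 and 3.4.5.3 define neither. They describe each time point separately, so excursions in different people at different times are never added up within a dose, and no one's worst change over the follow-up is tabulated.

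At stake is one component of a primary measure in a dose-escalation study. A reader comparing doses would have to build the count from the listing, with a threshold chosen after the data are seen.

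**Working it through.** **Inputs.** Cohorts of 4, with 3 EXT608 and 1 placebo, up to 6 cohorts (SAP 2.1.1). Placebo is pooled across cohorts (Protocol 8.3). A dose may be repeated in a second cohort (Protocol 3.1.5). Planned statistics are those of SAP 3.4.1.

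**The plan's own figure.** 6 × 4 = 24, which reproduces the approximately 24 evaluable participants: 6 × 3 = 18 on EXT608 and 6 × 1 = 6 on placebo. A dose arm is therefore 3, or 6 if repeated, and pooled placebo is 6 if six cohorts run. The design is not inferential, so there is no power figure to check.

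**Step 1: what one time point shows.** Take illustrative changes of 0, 0 and +40 mm Hg in an arm of three.
- Mean = 40/3 = 13.3.
- SD = √[((40 − 13.3)² + 2 × 13.3²)/2] = 23.1.
- Minimum 0, median 0, maximum 40.

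With three values, the minimum, median and maximum are the values themselves, so the single large change is visible. With changes of -40, 0 and +40 the mean is 0, but the minimum and maximum still show both extremes.

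**Step 2: what several time points show.** Compare two arms of three over three time points.

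| | Arm A: the same participant each time | Arm B: a different participant each time |
|---|---|---|
| Mean at each time point | 13.3 | 13.3 |
| SD at each time point | 23.1 | 23.1 |
| Min / median / max at each time point | 0 / 0 / 40 | 0 / 0 / 40 |
| Participants with any +40 change | 1/3 (33%) | 3/3 (100%) |
| Largest increase per participant | 40, 0, 0 | 40, 40, 40 |
| Mean largest increase | 13.3 | 40 |

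Every planned statistic agrees. The number affected and the participants' worst changes do not.

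**Step 3: arms of six.** For a repeated dose or pooled placebo, the minimum, median and maximum no longer give all values even at one time point, so the reconstruction in Step 1 is lost.

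**Step 4: what an added count would deliver.** Exact (Clopper-Pearson) 95% intervals:

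| Observed | Interval |
|---|---|
| 0/3 | 0 to 70.8% |
| 1/3 | 0.8 to 90.6% |
| 0/6 | 0 to 45.9% |
| 1/6 | 0.4 to 64.1% |

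The chance of at least one affected participant is 1 − (1 − p)ⁿ. For assumed true rates of 5%, 10%, 20% and 33% it is 14%, 27%, 49% and 70% with n = 3, and 27%, 47%, 74% and 91% with n = 6. The count would be descriptive only.

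**The case against.** A reader might infer more than the documents support, in two ways.

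**That the SAP reports only means, so a large change is averaged away.** It does not. SAP 3.4.1 adds the median, SD, maximum and minimum, and Step 1 shows that in an arm of three these reveal every value at a time point. The protocol also lists individual results, and with about 18 EXT608 recipients a listing can be read by eye. What the planned table cannot show is whether excursions at different times belong to the same person.

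**That blood-pressure harm, a listed potential DLT, goes uncounted.** Protocol 3.1.4 lists "Grade = 3 Hyper- and/or Hypotension", but as a treatment-emergent AE. Such an event therefore belongs in the AE output. SAP 3.4.5.1 lists all AEs and tabulates treatment-emergent events with numbers and percentages of participants. Protocol 6.5 does not itself send abnormal readings to the AE form, as 6.7 does for relevant ECG changes. However, the AE definition in 6.10.1.1 is wide enough to include a harmful pressure change. Evaluation of DLTs is left to the Safety Plan (Protocol 4.3.1.3). The DLT list is therefore no evidence of a gap here.

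The AE route still does not replace a vital-sign summary. It captures only changes judged to be AEs, it grades them mild, moderate or severe, and its tables are not required if the study has 5 or fewer treatment-emergent events.

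It can also be said that Protocol 8.3 itself assigns shift tables to laboratory data and values with changes to vital signs, so the SAP follows its protocol, and that counts out of three are imprecise. Both are true. Neither supplies the quantity the objective names.

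**Conclusion.** The point holds as a missing planned summary. For vital signs, the SAP text does not tabulate the number of participants affected across time points, or each participant's worst change, by dose. The constructed example bounds the loss in an arm of three: 1 of 3 and 3 of 3 affected can give the same planned table. The underlying values remain available in the listing, so this is a low-cost improvement. It does not threaten the safety review or the escalation decisions.

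Two conditions apply. The attached file of planned tables (SAP section 4) and the Safety Plan were not available, and either could contain a categorical vital-sign table; even so, SAP 3.3.4.2 defines no variable that would feed one. The 40 mm Hg changes and the event rates are illustrations, not trial figures.

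**What to change.** **SAP 3.3.4.2.** Define, for each participant over the post-dose readings to Day 28, the maximum increase and maximum decrease from the existing baseline in systolic pressure, diastolic pressure and pulse. State whether unscheduled readings count, since SAP 3.2.3.2 normally lists them without analysing them.

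**SAP 3.4.5.3.** Summarise these by EXT608 dose and pooled placebo, next to the statistics already planned. Add the number and percentage of participants in change or range categories fixed before unblinding.

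**Entry ranges.** The protocol's entry ranges (Protocol 4.2: "resting blood pressure outside the ranges of 90 to 140 mm Hg for systolic and 55 to 90 mm Hg for diastolic", and 40 to 90 bpm for heart rate) could serve as one descriptive reporting flag. They are eligibility criteria, so they should not be presented as severity grades or used as a clinical rule. Someone entering at 139 mm Hg systolic would be flagged after a rise of 2 mm Hg, while a fall from 135 to 95 would not be flagged. The worst-change summary should therefore carry the main information.

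**Cost.** SAP wording and one extra table from data already collected. Some trivial excursions will be flagged; the pooled placebo column gives them context. No dose, DLT or escalation rule changes. If the planned-tables file already contains such a table, only the variable definition needs adding.

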#### **3.4.5.4 ECG**

ECG at each time point and the corresponding Change from (section 3.3.4.3) baseline will be presented descriptively by treatment arm.

EXTBIO EXT608-101 Statistical Analysis Plan, V2, 2023-JULY-04

**3.4.5.5 *Injection site reaction***

Injection site reactions include VAS, tenderness, Edema and Erythema. The parameters defined in section 3.3.4.5 will be summarized descriptively by each treatment arm.

EXTBIO EXT608-101 Statistical Analysis Plan, V2, 2023-JULY-04

### **3.5 INTERIM ANALYSES FOR SAFETY REVIEW**

Interim analyses are planned for the safety review after each cohort. Blinded Interim summaries of selected variables are generated for the safety review committee. Details of those analyses are specified in the safety monitoring plan.

EXTBIO EXT608-101 Statistical Analysis Plan, V2, 2023-JULY-04

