##### 3.1.3 Staggering of Participants after Dose Escalation (Sentinel Participants)

For the first cohort, one participant will be dosed initially. A review of safety data, including Se-Ca and adverse events (AEs) for the first 72 hours post-dose will be conducted by the Investigator and Medical Monitor. If there are no safety concerns, a second participant will be dosed and the same safety review will be conducted to review data up to 72-hrs post-dose. If there are no safety concerns, the last two participants in the cohort will be dosed.

For subsequent cohorts, this staggering requirement only applies to cohorts for doses higher than previously experienced in the study.

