### 3.1.5 Dose Escalation

Dose escalation decisions will be based on the NCI Common Terminology Criteria for Adverse Events (CTCAE), Version 5.0 (2) and Se-Ca levels.

The DMB will review the seven-day safety data in each cohort before authorizing the initiation of the next cohort according to the following decision tree:

1. No Grade 3 AEs suspected related to study drug and no indication of effect observed from Se-Ca will result in the next dose at 3x the previous cohort dose.
2. No Grade 3 AEs suspected related to study drug and clear indication of effect on Se-Ca will result in the next dose at 2x the previous cohort dose.
3. A Grade 3 AE suspected related to study drug in a single (n=4) cohort and the absence of prohibitive effects on Se-Ca will result in an additional cohort at the same dose.
4. A single Grade 3 AE suspected related to study drug in 2 cohorts at the same dose (n=8) cohort and the absence of prohibitive indication of effects on Se-Ca will result in a dose escalation to 1.5x the previous dose.
5. Two or more of the same Grade 3 AE within the same cohort suspected related to study drug, or average peak Se-Ca > 1.5 mg/dl above the Upper Limit of Normal (ULN) range will terminate dose escalation.
  - a. If the last dose escalation was 50% and by implication 2 cohorts received the previous dose for an n=8, the study will stop.
  - b. If the last dose escalation was >50%, the next cohort should receive a dose 2/3x the previous dose.

Any DMB recommendation that deviates from the decision tree will be ratified by the Sponsor prior to implementation.

The study schematic is presented in [Section 3.2](#).

[figure not shown]

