### 8.2 Analysis populations

Two participant populations will be defined. The Safety of Full Analysis Set population (FAS) will be defined as all participants who are randomized. The Per-Protocol (PP) population will be participants for whom evaluable data to and including Day 7 is available and with no major protocol violations.

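### Rule 5 does not say whose peak calcium is averaged, and SAP 3.5 and the protocol disagree on blinding; if the placebo participant is pooled in, the 1.5 mg/dl stop fires only when the actives average more than about 2.0 above ULN

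*SAP*

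**What the plan says.** Protocol 3.1.5, repeated in the synopsis, governs escalation through a five-rule tree. It opens with "The DMB will review the seven-day safety data in each cohort", to be done before the next cohort is authorised. The calcium limb of rule 5 reads "average peak Se-Ca > 1.5 mg/dl above the Upper Limit of Normal (ULN) range will terminate dose escalation". Nothing in the rule says which participants enter the average.

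Each cohort has three EXT608 participants and one placebo participant (protocol 3.1.1). The AE rules in the same tree give cohort size with placebo included: rule 3 starts "A Grade 3 AE suspected related to study drug in a single (n=4) cohort", and rule 4 uses n=8 for two cohorts at one dose.

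The documents differ on what the reviewing body sees:

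- Protocol 5.4.1 exempts DMB members from the treatment blind.
- Protocol 7.3.2 promises the DMB a summary of the cohort's data and does not mention a split by arm.
- Protocol 8.3 states "All summaries will be performed by placebo and each EXT608 dose level" and "DMB data packages will be based on the FAS for safety and PP for PK/PD".
- Protocol 8.2 defines the safety set: "The Safety of Full Analysis Set population (FAS) will be defined as all participants who are randomized". The per-protocol set requires evaluable data to Day 7 and no major violation. Neither set leaves placebo out.
- SAP 3.5, on the review after each cohort, states "Blinded Interim summaries of selected variables are generated for the safety review committee". It leaves the detail to a safety monitoring plan that is not among the documents.
- SAP 1.4 declares no modification of the protocol's statistical section.

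**The concern.** Rule 5 is meant to stop escalation on drug effect, and a placebo participant's calcium says nothing about that. If the review works from a blinded summary, the one average available is over all four participants, and a placebo value in the normal range pulls it down. A dose whose actives already average more than 1.5 mg/dl above ULN could then pass the calcium limb. With no related Grade 3 AE and a clear calcium effect, rule 2 would double that dose. With one such AE, rule 3 would repeat it, provided the calcium effect is not judged prohibitive.

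Following protocol 5.4.1 instead allows the actives' mean to be computed, but at another cost. The Investigator and the Medical Monitor are voting DMB members (protocol 7.3.1) and would see treatment assignments from the Day 7 review onwards. AEs are assessed to Day 28, and protocol 3.3.5 relies on the double blind to limit bias in AE reporting. The plan should choose one route and say how it is carried out.

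**Working it through.** **The plan's own figure.** The 1.5 mg/dl margin is a chosen limit with no stated derivation, and the sample size is not inferential, so there is no calculation to reproduce. The one count that can be checked agrees: 6 cohorts × 4 = 24, matching the roughly 24 evaluable participants planned.

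**Inputs.** The threshold is 1.5 mg/dl above ULN (protocol 3.1.5). The cohort is 3 active and 1 placebo (protocol 3.1.1). Entry calcium must be within laboratory normal limits (protocol 4.1, criterion 8), but those limits are not given in mg/dl. The placebo peak is therefore an assumption and is varied below.

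**Formula.** Let A be the mean peak of the actives and p the placebo peak, both in mg/dl relative to ULN. The mean of four is (3A + p)/4. It exceeds 1.5 when 3A + p > 6, that is, when A > 2.0 − p/3. Two cohorts at one dose (6 active, 2 placebo) give the same result when p is the mean placebo peak.

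| Placebo peak relative to ULN | Actives must average more than | Mean of four when actives average exactly 1.5 |
|---|---|---|
| 0 | 2.00 | (4.5 + 0)/4 = 1.125 |
| 0.5 below | 2.17 | (4.5 − 0.5)/4 = 1.00 |
| 1.0 below | 2.33 | (4.5 − 1.0)/4 = 0.875 |

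Outside that range, a placebo peak 0.5 above ULN gives 1.83 and one 1.5 below gives 2.50. Pooling raises the effective limit for any placebo peak less than 1.5 above ULN, and raises it by at least 0.5 for any placebo peak at or below ULN.

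**Example.** Active peaks of 2.2, 1.8 and 1.7 above ULN average 5.7/3 = 1.90, so escalation stops. With placebo at 0, 0.5 below or 1.0 below, the mean of four is 5.7/4 = 1.43, 5.2/4 = 1.30 or 4.7/4 = 1.18, so it does not.

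**Illustration of how often this matters.** Assume independent normal values, a true active mean of 2.0 with SD 0.5, and a placebo mean 0.5 below ULN with SD 0.3.

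- Actives only: mean 2.0, SE 0.5/√3 = 0.289. The chance of exceeding 1.5 is 96%.
- All four: mean (6.0 − 0.5)/4 = 1.375, SE √(3 × 0.25 + 0.09)/4 = 0.229. The chance is 29%.
- For an active SD of 0.3 to 0.8, the ranges are over 99% down to 86% on actives and 20% to 36% on all four.
- At a true active mean of 2.5 (SD 0.5), the contrast narrows to over 99% against about 86%.

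**The case against.** A reader might infer that rule 5 requires the mean of the three actives and that the SAP overrides this. The text does not go that far. Rule 5 is silent on the denominator, and the n=4 and n=8 labels give cohort sizes; they do not settle whose calcium is averaged. The actives' mean is the sensible reading for a limit on drug effect, but it remains a reading.

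A reader might also infer that the DMB will in fact work from a pooled mean. That is not established either. Protocol 5.4.1 and 8.3 both favour a split by arm, SAP 2.1.2 concerns code access at allocation and not what the DMB receives, and the unseen safety plan may settle the matter. Blinded could also mean masked arm labels. That last defence is weak in a 3:1 cohort, because group sizes of 3 and 1 identify the placebo participant at once. A summary that is truly blinded must pool all four or list them without assignment, and neither yields the actives' mean.

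The strongest counter-argument is that other protections exist, and it stands in part. Protocol 5.4.2 blinds no outcomes, laboratory reports go to the site, and the Investigator and Medical Monitor review calcium during staggered dosing (3.1.3). Three high peaks and one normal one would be noticed. Grade 3 hypercalcemia is a listed DLT, two related Grade 3 AEs of the same kind in a cohort end escalation whatever the mean, and the DMB may depart from the tree with Sponsor ratification. It would therefore be wrong to say that escalation past the limit follows automatically. But the calcium limb is joined to the AE limb by an or, so it is meant to work alone, and none of these protections defines its average.

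**Conclusion.** Wrong as written. The rule 5 average is undefined, and SAP 3.5 contradicts protocol 5.4.1 and 8.3 on whether the escalation review is blinded, with no modification declared. If SAP 3.5 is followed and all four participants are averaged, the effective limit for the actives rises from 1.5 to more than 2.0 mg/dl above ULN with the placebo peak at ULN, to 2.17 at 0.5 below and to 2.33 at 1.0 below.

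The algebra is exact; the placebo peak is assumed. A reader might take 2.5 as the headline figure, but that needs a placebo peak 1.5 mg/dl below ULN, and a peak is the highest of repeated samples. The probabilities depend on the chosen means and SDs and only illustrate the effect. The calcium limb is weakened, but individual results and the AE rules remain as partial safeguards. The point should be corrected.

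**What to change.** 1. In protocol 3.1.5 and the matching synopsis text, state that rule 5 uses the mean of each individual's highest post-dose Se-Ca up to Day 7, taken over the EXT608-treated participants at that dose, with placebo excluded.
2. In SAP 3.5, state that the DMB's independent statistician receives the treatment codes, computes this mean and reports to the DMB whether the limit is met.
3. Align protocol 5.4.1 and SAP 3.5 on which DMB members see unblinded data. This matters because the Investigator and the Medical Monitor vote.

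The cost is a few sentences of amendment and one small unblinded computation per cohort. It needs no new samples, and the independent statistician is already a DMB member under protocol 7.3.1.
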